Participants

The initial sample of respondents (n=350) was recruited through an open project application lasting two months (from 1 July 2021 to 1 September 2021), from which 300 preschool children aged 4–7 were selected for this randomized, controlled intervention study. The recruitment process was completed after the selection process, and the optimal sample of subjects was filled out. The study sample underwent stratified randomization, resulting in the division into either EG (Experimental Group - 1) or CG (Control Group - 2). When stratifying, researchers used proportionate sampling to maintain the correct proportions of genders in every group. The intervention program started with a group of 150 children in EG, and at the same time, 150 children in CG started a kindergarten educational program in a Preschool Institution. Throughout the nine months of the experimental program, 51 children from the intervention group and 29 from the control group were excluded from the final analyses due to injury, flu, illness, or attendance at classes falling below 80%. Finally, 99 children (54 boys & 45 girls) who composed the EG and 121 children (64 boys & 57 girls) who composed the CG were analyzed for the effects of the DG. After nine months, a total of 220 participants were included in the final analysis. The parents or guardians of each child provided written informed consent, and the study received approval from the institutional ethics committee at the Faculty of Sport and Physical Education, University of Novi Sad (ethical approval number: 46-06-04/2020-1).

[figure not shown]
The exclusion criteria were:

- History of neurological or musculoskeletal disorders
- Clinical conditions that could affect balance, such as motor disorders, diabetes, heart disease, stroke, vision problems, thyroid issues, or issues with nerves or blood vessels.

The inclusion criteria for this study were:

- No injuries within the past six months
- No other medical conditions, including COVID-19
- No scheduled physical activity in the previous three months
- Considered valid for the experimental programs if participants completed at least 80% of all training sessions.

Figure 1 illustrates the flow of participants through the study.

Testing procedures

Secondary outcome – Anthropometric measures

Anthropometric data, including height and weight, were collected before the motor competence and physical fitness assessment. Following Martin's guidelines, body height was measured using a fixed anthropometer (GPM Anthropometer 100; DKSH Switzerland Ltd., Zurich, Switzerland; ± 0.1 cm). Body mass was measured with a digital balance (BC1000, Tanita, Japan; ± 0.1 kg), following the guidelines proposed by the International Biological Program (IBP). The body mass index (BMI) was calculated using the weight/height 2 (kg/m 2) formula based on the provided height and weight values.

Primary outcome - TGMD-2

The Test of Gross Motor Development – 2 (TGMD-2) is a standardized test to assess gross motor functioning in children aged 3 through 10. Researchers have previously utilized the TGMD-2, which demonstrates high reliability and minimal test error, instilling confidence in its application (Butler et al., 2023; Lopes et al., 2018; Nagy et al., 2023). The TGMD-2 measures 12 fundamental motor skills divided into two subcategories. The locomotor subtest consists of six skills: run, hop, gallop, leap, horizontal jump, and slide. The object control subtest includes six skills: hitting a stationary ball, dribbling while stationary, catching, kicking, throwing overhand, and rolling underhand. Motor competence was assessed with the TGMD-2 using the detailed instruction manual by examiners trained in physical education with prior experience in TGMD-2 measurements (Ulrich, 2000). Experienced researchers in test assessments coordinated and supervised the assessments. Each test took approximately 15-20 minutes and was performed indoors. The assessments were carried out, recorded, and coded at the Gymnastics Center, Faculty of Sport and Physical Education, University of Novi Sad, Serbia, from 1. September 2021 to 15. September 2021. Following a visual demonstration, each participant performed all 12 skills of the TGMD-2, receiving one practice attempt and two assessment trials for each skill. Each skill

consists of three to five performance criteria, with one score assigned if the criterion is present and zero if not. Total scores for each skill and subtest were calculated, ranging from 0 to 48.

Interventions

The Developmental Gymnastics Exercise Program

The nine-month DG exercise program (from 15 September 2021 to 15 May 2022) was conducted indoors in a well-equipped gymnasium. Trained physical education teachers and gymnastics experts led the training sessions twice weekly (on Tuesday and Thursday) without a break throughout the experimental period. Each session lasted for 60 minutes and covered a range of gymnastics activities and exercises, with each week focusing on specific categories of GMS, such as stability (trunk strength), locomotor skills (running, hopping, skipping), and manipulation (ball skills). The program also introduced children to fundamental elements of DG and was meticulously structured, incorporating frontal and group work, primarily circuit training (polygon) or repetitive (station) training. Obstacle courses were designed to incorporate various gymnastic apparatus and props, encouraging problem-solving through gymnastic and athletic exercises and elementary games. The number of repetitions, sets, and complexity of exercises and routines gradually increased in the central part of the session as children could perform them quickly, accompanied by external cues such as sweating, blushing, spontaneous breaks, and heart rates. The training structure consisted of three parts: I) A 15-minute warm-up with diverse movements, speed-varied exercises, activities for flat feet, stretching, corrective and preventive exercises for posture improvement, and a focus on proper performance awareness. II) The central part lasted 40 minutes and included reviewing and practising previous skills, introducing and practising new skills, engaging in competitive activities, and conditioning exercises. III) A 5-minute cool-down involving stretching, coaching feedback, and informal discussion about sports, exercise, and daily activities. A positive and friendly atmosphere was maintained throughout each training session, accompanied by suitable kids' music, especially during the

introduction and preparation phases. Basic principles and procedures were adapted from previous research (Bala, 1996; Radanovic, 2018).

In contrast, the CG adhered to their routine, engaging in three structured extracurricular physical activity sessions per week, each lasting approximately 45 minutes. A physical education specialist and a kindergarten teacher led these sessions. They were designed to enhance fundamental locomotor skills (e.g., hopping, skipping, jumping, crawling, and navigating obstacles) and manipulative skills involving balls, bricks, and toys. The primary objective was to create an environment where children could enjoy and have fun during exercise. According to the National Program for Kindergarten Physical Education Classes, the standardized program predominantly featured frontal and group activities, encompassing traditional games and dances, and included different training forms. The authors did not thoroughly provide detailed information about the intervention program.

Statistical analyses

Unless otherwise specified, we present data as mean and 95% confidence intervals [95% CIs]. We conducted an independent samples t-test to examine whether the baseline study outcomes varied among the groups. Normality was confirmed using the Kolmogorov-Smirnov test, and homogeneity of variances and covariance matrices were accepted through Levene's and Box's tests, respectively. We first modelled raw scores of each study outcome using a 2x (girls vs. boys), 2x (EG vs. CG), and 2 (initial vs. final testing) mixed ANCOVA (Model 1) to test confounding effects of gender, age, and BMI on intervention effects. We inspected the main effects of gender, age, and BMI to assess whether the study outcomes depended on these factors. This examination aimed to determine whether gender, age, and BMI could control the effects of the DG program on the study outcomes. Hence, respecting the significance of control variables effects ($p \leq 0.05$), we modelled each study outcome using either a 2x (girls vs boys) 2x (EG vs CG) 2 (initial vs final testing) mixed ANCOVA with age and BMI or only with age to find whether study outcome mean changes [95% CIs] from initial to final testing depended on whether subjects completed DG program or not (Model 2). We assessed potential gender confounding effects on changes in the study outcomes by

examining a time*group*gender interaction effect, followed by a time*group interaction effect for boys and girls, respectively. The time*group interaction effects allowed the evaluation of DG program effects followed by the simple main effects of time, which designated mean changes [95% CIs] from initial to final testing for each group. In addition, we estimated the parameters (beta coefficients, β and partial η^2 , η^2) of ANCOVA models. Games-Howel tests corrected multiple comparisons, and a p-value of ≤ 0.05 designated statistical significance. Partial eta squared (partial η^2) is reported as a measure of effect size and classified as small (0.01), medium (0.06), and large (0.14), according to Cohen. We conducted all analyses using SPSS (v.23, IBM Corporation, New York, USA).

References

Bala, G. (1996). *Sportska školica - Razvoj motoričkog ponašanja dece* (Sports school - Development of children's motor behavior). Kinesis.

Butler, L. S., Sugimoto, D., Erdman, A., Yoder, J., Greiner, K., Larroque, C., Latz, K., Loewen, A., Wyatt, C. W., DeVerna, A., & Ulman, S. (2023). Highly Active Middle School Athletes Demonstrate Poor Motor Skill Proficiency. *Sports Health*, 19417381231178822. <https://doi.org/10.1177/19417381231178822>

Lopes, V. P., Saraiva, L., & Rodrigues, L. P. (2018). Reliability and construct validity of the test of gross motor development-2 in Portuguese children. *International Journal of Sport and Exercise Psychology*, 16(3), 250-260. <https://doi.org/10.1080/1612197X.2016.1226923>

Nagy, Á., Wilhelm, M., Győri, F., Domokos, M., & Berki, T. (2023). Assessment Tools Measuring Fundamental Movement Skills of Primary School Children: A Narrative Review in Methodological Perspective. *Sports*, 11, 178. <https://doi.org/10.3390/sports11090178>

Radanovic, D. (2018). *The effects of the developmental gymnastics program on the development of motor skills and abilities and morphological characteristics of preschool children* University of Novi Sad]. Novi Sad.

Ulrich, D. (2000). *Test of gross motor development-2*.

UNIVERSITY OF NOVI SAD
FACULTY OF SPORT AND PHYSICAL EDUCATION
ETHICS COMMITTEE – COMMISSION

DECISION No. 46-06-04/2020-1

ETHICS COMMITTEE - COMMISSION FOR THE IMPLEMENTATION OF SCIENTIFIC
PROJECT - RESEARCH

DESCRIPTION

After reviewing the submitted application (on June 17, 2020) for a scientific research project entitled: **Biomechanical parameters of athlete's postural stability**

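### The analysed set is ambiguously defined: injury, flu and illness stand beside the 80% attendance rule as undefined post-randomisation reasons for removing children

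*Protocol*

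**What the plan says.** Everything that decides who is analysed is in the Participants section of the Protocol.

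- **Start of the programme.** "The intervention program started with a group of 150 children in EG", and "150 children in CG started a kindergarten educational program in a Preschool Institution".
- **Losses.** Over the nine months, 51 EG and 29 CG children "were excluded from the final analyses due to injury, flu, illness, or attendance at classes falling below 80" per cent. The sentence gives no duration, severity or diagnostic threshold for injury, flu or illness.
- **Validity.** The last item in the list of inclusion criteria reads: "Considered valid for the experimental programs if participants completed at least 80% of all training sessions". It names attendance only.
- **Neighbouring item.** The same list contains "No other medical conditions, including COVID-19", with no time frame.
- **Analysed.** "99 children (54 boys & 45 girls) who composed the EG" and "121 children (64 boys & 57 girls) who composed the CG", 220 in total.

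The section on the gymnastics programme sets EG sessions on Tuesdays and Thursdays, without a break, from 15 September 2021 to 15 May 2022. Controls had three sessions a week.

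**The concern.** The two statements share the 80% threshold but not the list of conditions. In the validity item, attendance is the only thing that matters after the start. In the exclusion sentence, low attendance is one of four reasons joined by *or*. If injury, flu and illness counted only through missed sessions, the attendance reason would already cover them. Listing them separately suggests that they could act on their own, but the sentence does not say so.

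The two statements also differ in scope. The validity item speaks of experimental programmes and training sessions. The exclusion sentence speaks of classes and is applied to both arms. Which sessions form the denominator for a control child is not stated.

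At stake is who enters the comparison. Injury, illness and attendance all occur after randomisation and may be related to the arm and to motor development. If a health event alone can remove a child who attended and was tested, the analysed set is selected on an undefined event, and another team could not rebuild it from the Protocol. The uncertainty would remain if the set were used only for a supportive analysis.

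**Working it through.** **1. The Protocol's own flow (Participants section).**

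- EG: 150 − 51 = 99; by sex 54 + 45 = 99.
- CG: 150 − 29 = 121; by sex 64 + 57 = 121.
- Total: 99 + 121 = 220, as stated.

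The counts are consistent. The question is what rule produced them.

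**2. Can a child meet the 80% item and still have a listed health reason?** Inputs: the Tuesday/Thursday schedule and the two programme dates.

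- Thursdays from 16 September 2021 to 12 May 2022: 35. Tuesdays from 21 September 2021 to 10 May 2022: 34. Total 35 + 34 = 69, assuming no session was cancelled.
- Sessions needed: 0.8 × 69 = 55.2, so 56. Sessions that may be missed: 69 − 56 = 13.
- Illustration, two weeks away: (69 − 4)/69 = 94.2% attendance.
- Illustration, four weeks away: (69 − 8)/69 = 88.4% attendance.

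Both illustrative children meet the attendance item, and both have a reason that the exclusion sentence lists. The overlap is therefore possible in EG. No count is made for CG, because the Protocol gives a weekly frequency for that arm but no session calendar.

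**3. Size of the losses that the statements govern.**

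- EG: 51/150 = 34.0%. CG: 29/150 = 19.3%. Overall: 80/300 = 26.7%.
- Difference: 34.0 − 19.3 = 14.7 percentage points.
- Standard error: √(0.340 × 0.660/150 + 0.193 × 0.807/150) = 0.0504.
- 95% CI: 14.7 ± 1.96 × 5.04, that is 4.8 to 24.5 points.
- Chi-square: 300 × (51 × 121 − 99 × 29)² / (150 × 150 × 80 × 220) = 8.25, p = 0.004. With continuity correction p = 0.006; Fisher's exact test p = 0.006.

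**4. How many children does the ambiguity affect?** The text does not split the 80 by reason, so only logical bounds are available. If no excluded child had both at least 80% attendance and a final TGMD-2 score, the set stays at 220. If all had both, it would be 220 + 80 = 300. The upper bound would require that nobody was removed for low attendance, so it is a limit and not an expectation.

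**The case against.** The strongest reply is that there is no conflict. The threshold is the same in both places. The validity item is the last in a list with health conditions, and nothing says that 80% attendance is sufficient for being analysed. Read as a necessary condition, it sits comfortably beside other reasons for exclusion. The exclusion sentence is a report in the past tense, and injury, flu and illness may simply be why children left the programme or missed the final test. Such children might have no final score to analyse.

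This stands as far as it goes. A reader might infer that the Protocol declares the same child both valid and excluded, or that any brief illness led to removal. The text supports neither: it does not mention brief illness, and the first inference follows from only one reading. What remains is that the text allows both readings and does not choose between them.

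Three further inferences also lack support:

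- **Staff who knew the arm chose whom to exclude.** The Protocol does not say who decided, when, or with what knowledge.
- **A definite number of compliant, tested children was lost.** Any such figure restates an assumption, and zero fits the text.
- **Counts by reason were withheld.** They may be in the participant-flow figure, which is missing from the copy reviewed.

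Two practical objections remain. Detailed analysis-set definitions are often left to an SAP. Here, however, the Protocol itself states the rule, and states it ambiguously. The Protocol is dated March 2024 and the programme ended in May 2022, so a change now would come after the data were collected. That is correct, and it is a reason to label the change openly.

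**Conclusion.** The point holds as an ambiguity, not as a contradiction. The Protocol does not settle whether a randomised child with at least 80% attendance and a health event is analysed. It also lists undefined post-randomisation health events as reasons for removal beside attendance. Together these reasons account for 80 of 300 children, with losses 14.7 points higher in EG (95% CI 4.8 to 24.5).

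That imbalance does not show that the health reasons were applied unevenly, since differences in attendance alone could produce it. It does mean that the definition of the set matters for the comparison. The effect of the ambiguity on the number analysed is unknown and may be nil.

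The overlap in EG rests on the stated dates and on no session having been cancelled. Attendance-based selection is itself a problem that clearer wording would not cure, so the fix has to go beyond wording.

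**What to change.** 1. **Reconcile the two statements** in the Participants section so that one definition applies, and move the attendance condition out of the inclusion criteria, since it cannot be known at enrolment.
2. **Do not use injury, flu or illness as separate reasons** to drop a randomised child who has a final TGMD-2 score.
3. **Make the main analysis that of all randomised children with a final score**, in the arm to which they were randomised.
4. **Define any completer set in both arms by one rule only**: at least 80% of the sessions scheduled for the child's arm, derived from attendance records without sight of final scores. Present it as supportive, because an attendance-only rule still selects after randomisation.
5. **Report the 80 exclusions by reason and arm**, and state how many had at least 80% attendance and how many had a final score.
6. **Date the change and label it** as made after data collection, and show the analysis of the 220 beside it.

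The cost is rewording and re-derivation of the sets, provided attendance records were kept; the Protocol does not mention registers, although an 80% rule implies them. Including children who were unwell for part of the programme may slightly dilute the completer estimate. Children without a final score remain missing, and the fix does not recover them.

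### Model 1 decides whether age and BMI bear on the programme effect from their main effects, which describe average score level, although the programme effect is a difference in change; in practice this settles only whether BMI stays in Model 2

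*Protocol*

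**What the plan says.** All of this stands in the Protocol under Statistical analyses.

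- **Purpose of Model 1:** "to test confounding effects of gender, age, and BMI on intervention effects".
- **Terms inspected:** "We inspected the main effects of gender, age, and BMI to assess whether the study outcomes depended on these factors".
- **Inference to be drawn from them:** "This examination aimed to determine whether gender, age, and BMI could control the effects of the DG program on the study outcomes".
- **Consequence:** "Hence, respecting the significance of control variables effects", at p ≤ 0.05, Model 2 becomes a "mixed ANCOVA with age and BMI or only with age to find whether study outcome mean changes" depend on the programme. Gender is a factor in both versions.
- **Programme effect:** "The time*group interaction effects allowed the evaluation of DG program effects".
- **Gender on change:** potential confounding by gender is assessed by "examining a time*group*gender interaction effect, followed by a time*group interaction effect for boys and girls, respectively".

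No interaction of age or BMI with time, or with time and group, is named.

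**The concern.** The question asked is about change and the term inspected is about level. A covariate that raises both scores equally has a strong main effect and drops out of the difference between them. A covariate that acts on change can have almost no main effect. Main-effect significance is therefore a poorly matched rule for choosing what to adjust time*group for, and it cannot show whether a covariate confounds or modifies the programme effect.

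Two things are at stake. BMI may be kept where it does nothing for the programme effect, or dropped where it predicts change. The report may also state that age or BMI does, or does not, control the programme effect on the strength of a test of something else. For raw motor scores in children aged 4 to 7, a main effect of age is to be expected whatever age does to the programme effect.

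**Working it through.** The Protocol gives no figure to reproduce on this point. The check is algebra, followed by sizes under stated assumptions.

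**Inputs from the Protocol.** 99 and 121 children analysed (150 − 51 and 150 − 29, Participants section); two testings; threshold 0.05.

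**Assumptions.** Residual SD 1 at each testing, initial–final correlation 0.7, covariate in SD units, true time*group effect 0.30 SD.

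**Step 1, algebra.** Let the covariate slope be b0 at initial and b1 at final testing. The two-time-point model separates into two regressions:
- on (initial + final)/2, where the covariate's slope is (b0 + b1)/2: its main effect;
- on final − initial, where its slope is b1 − b0: time*covariate. Time*group and time*group*covariate also belong here.

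Either slope can be zero while the other is not. This step needs none of the assumptions.

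**Step 2, how often the screen keeps a covariate.** The SD of the mean score is √((1 + 0.7)/2) = 0.922, so the main-effect slope has standard error of about 0.922/√220 = 0.062. Simulation gives:

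| b0, b1 | Main-effect slope | Change slope | Main effect p ≤ 0.05 | time*covariate p ≤ 0.05 |
|---|---|---|---|---|
| 0.2, 0.2 | 0.20 | 0 | 89% | 5% |
| 0, −0.3 | −0.15 | −0.3 | 66% | 100% |
| 0.1, −0.2 | −0.05 | −0.3 | 12% | 100% |
| −0.15, 0.15 | 0 | 0.3 | 5% | 100% |

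**Step 3, effect modification.** Let the final slope differ by m in the gymnastics group (share 99/220 = 0.45), with b0 = b1 = b. The main-effect slope is then about b + 0.45 × m/2.
- b = 0.1, m = −0.3: 0.1 − 0.0675 = 0.0325; main effect significant in 8%.
- b = 0.1, m = +0.3: 0.1 + 0.0675 = 0.1675; significant in 76%.
- b = 0, m = +0.3: 0.0675; significant in 19%.

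Time*group*covariate is significant in about 80% in all three. The main effect's result depends on the sign and size of b, not only on the modification.

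**Step 4, cost with a balanced covariate.** The two-step time*group estimate averages 0.30 in every pattern tried. For power, the SD of change is √(2 × 0.3) = 0.775 and the group-contrast factor is √(1/99 + 1/121) = 0.1355.
- Adjusted: standard error 0.775 × 0.1355 = 0.105; 0.30/0.105 = 2.86; power about 81%.
- A covariate with change slope 0.3 left out: SD √(0.6 + 0.09) = 0.831; standard error 0.1126; 0.30/0.1126 = 2.66; power about 76%.

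The ceiling is thus about 5 to 6 points. In simulation, the screen costs about 2 points for slopes 0/−0.3 (79% against 81%) and about 5 for 0.1/−0.2 (75% against 80%). Keeping a covariate unrelated to change costs nothing visible.

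**Step 5, bias with an unbalanced covariate.** Shift in time*group = change slope × group difference on the covariate. With 0.3 and an assumed 0.3 SD difference, this is 0.09, so the unadjusted estimate is 0.39. If the screen keeps the covariate in 5% of trials, the two-step average is 0.05 × 0.30 + 0.95 × 0.39 = 0.386 (simulated 0.38 to 0.39). Adjustment returns 0.30. Chance imbalance alone has an SD of 0.1355, giving a typical shift of 0.3 × 0.1355 = 0.04. If the covariate acts on level only, the estimate is 0.30 with or without it, even with the 0.3 SD imbalance.

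**The case against.** **The screen decides little.** Age and gender are in both versions of Model 2, and gender is examined on change with the right kind of term. This stands: only BMI can be dropped, and a reader who infers that the whole of Model 2 is built on faulty selection goes beyond the text.

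**The numerical consequences are mild.** This also stands. With balance there is no bias and the power loss is small. The largest failures of the screen need particular patterns, such as a slope that reverses sign between September and May, or a modification opposite in sign to the slope. A reader might infer that main effects carry no information on change. That is too strong: a covariate acting only at final testing passes the screen in about two thirds of trials. The accurate statement is that the main effect does not test the relation to change.

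**The wording may be loose.** The sentence on main effects speaks of dependence of outcomes, which main effects do answer, and the word control may mean no more than adjustment. This is fair for that sentence alone, but the stated purpose of Model 1 is confounding of intervention effects, and the selection rule follows from it.

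**The time interactions may be in the model unstated, or left to an analysis plan.** Possible, so their absence is not established. It does not rescue the rule. If time*BMI enters along with BMI, a p-value about level decides whether change is adjusted for BMI. If it does not enter, adding BMI leaves time*group untouched. The Protocol itself fixes the criterion and the threshold, so this is a stated choice and not an omission.

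**Conclusion.** The point holds in a narrow form. The term inspected in Model 1 does not answer the question put to it, and BMI's place in Model 2 rests on that term. Any statement that age or BMI does or does not control the programme effect would rest on the wrong test; for age this is a matter of interpretation only, since age is always in the model.

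The mismatch between level and change is algebraic and certain. The sizes are conditional on the assumed slopes, the correlation of 0.7 and a 0.30 SD effect: no bias and at most about 5 to 6 points of power with a balanced covariate, and 0.38 to 0.39 against 0.30 in the example with a 0.3 SD imbalance.

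A reader might infer that the trial's programme estimate is biased. The Protocol does not support that. Exclusions after randomisation were unequal (51/150 = 34% and 29/150 = 19%), so randomisation no longer guarantees balance in the analysed groups, but no BMI imbalance and no relation of BMI to change is shown.

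**What to change.** 1. Delete the main-effect screen and the significance-based choice between the two versions of Model 2.
2. For every TGMD-2 score, fit one fixed Model 2 with gender, age at initial testing and BMI at initial testing, each with its interaction with time. Keep time*group as the programme effect and time*group*gender as planned.
3. Remove statements on confounding or control that rest on main effects.
4. If modification by age or BMI is to be claimed, base it on time*group*age and time*group*BMI, report these with 95% CIs, and label them exploratory.

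The cost is revised wording and a rerun on data already collected. The model for change has 220 − 4 − 2 = 214 error degrees of freedom; the fixed model uses one more than the reduced version if only time*BMI is new, or two if time*age is new as well. Some p-values will shift slightly.

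### The programme effect is read from time-by-group, a change-score comparison; the initial score is never a covariate, which is valid under randomisation but usually costs precision

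*Protocol*

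**What the plan says.** The Statistical analyses section models the raw initial and final scores together in a gender by group by time mixed ANCOVA, so the initial score is part of the response. The programme effect is then read from one term: "The time*group interaction effects allowed the evaluation of DG program effects". The same contrast is repeated within gender, "followed by a time*group interaction effect for boys and girls, respectively". The intervals described are those of the simple main effects of time, "which designated mean changes [95% CIs] from initial to final testing for each group".

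The only other stated use of the initial score is a baseline comparison: "We conducted an independent samples t-test to examine whether the baseline study outcomes varied among the groups". No adjustment follows from it.

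Covariates are chosen in two stages. Model 1 is fitted "to test confounding effects of gender, age, and BMI on intervention effects", and the terms examined are described thus: "We inspected the main effects of gender, age, and BMI to assess whether the study outcomes depended on these factors". Model 2 is then a "mixed ANCOVA with age and BMI or only with age to find whether study outcome mean changes" depended on the programme, with the choice made for each outcome at p ≤ 0.05.

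The Participants section gives the analysed numbers: "99 children (54 boys & 45 girls) who composed the EG and 121 children (64 boys & 57 girls) who composed the CG".

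**The concern.** The label ANCOVA suggests baseline adjustment, but the listed covariates show there is none. With two occasions, the time-by-group term uses the initial score only by subtracting it in full. Unless the true slope of final on initial score is 1, this is less efficient than estimating the slope, and the data needed to do better are already in hand. The loss matters most in the boys-only and girls-only comparisons, which are the smallest.

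The point also bears on interpretation. After randomisation 51/150 (34.0%) were excluded from the experimental group and 29/150 (19.3%) from the control group, so balance at the initial test is not assured in the analysed set. A change-score and a baseline-adjusted estimate treat any imbalance differently, and a reader shown only one cannot tell how far the result depends on it.

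The BMI rule is secondary. A main effect of BMI concerns the average of the two scores, whereas a between-child covariate alters time-by-group only through its interaction with time. The text does not exclude that such interactions were also screened. Either way, the covariate set is not the same for every outcome.

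**Working it through.** **Inputs.** From the Participants section: 150 − 51 = 99 and 150 − 29 = 121, together 220; boys 54/64, girls 45/57. From Statistical analyses: the contrast, the covariates and the 0.05 level (taken as two-sided). Assumed, because the Protocol gives neither: r, the initial-final correlation, and k = final SD / initial SD, both given age and gender. There is no stated power or precision figure to reproduce.

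**Step 1: what the contrast is.** On simulated data, the time-by-group term with covariate-by-time terms and the group coefficient from regressing (final − initial) on the same covariates gave the same estimate and standard error (0.2576, 0.1195). The slope on the initial score is therefore fixed at 1.

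**Step 2: variances.** With s₀ and s₁ the initial and final SDs:

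- change: s₀² + s₁² − 2·r·s₀·s₁
- adjusted: s₁²(1 − r²)
- difference: (s₀ − r·s₁)², never negative, and zero only when r·s₁/s₀ = 1 (for example r = 0.8 with k = 1.25)

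The SE ratio, change to adjusted, is √[(1 + k² − 2rk) / (k²(1 − r²))]. For k = 1 it is √[2/(1 + r)], and the equivalent sample size is 220(1 + r)/2. At r = 0.5 these are √(2/1.5) = 1.155 and 220 × 0.75 = 165.

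SE ratio, with the number of adjusted children giving the same precision as 220 on change scores:

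| k | r = 0.3 | r = 0.5 | r = 0.7 | r = 0.9 |
|---|---|---|---|---|
| 1.0 | 1.240 (143) | 1.155 (165) | 1.085 (187) | 1.026 (209) |
| 1.2 | 1.146 (168) | 1.072 (192) | 1.017 (213) | 1.012 (215) |
| 0.8 | 1.411 (110) | 1.323 (126) | 1.262 (138) | 1.282 (134) |

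**Step 3: interval widths, equal SDs.** The half-width in SD units is t × √(1/n₁ + 1/n₂) × √[2(1 − r)] for change and t × √(1/n₁ + 1/n₂) × √(1 − r²) for adjusted. The values of √(1/n₁ + 1/n₂) are 0.1355, 0.1848 and 0.1994, with t = 1.971, 1.981 and 1.985.

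| Change v adjusted | r = 0.3 | r = 0.5 | r = 0.7 |
|---|---|---|---|
| All, 99/121 | 0.32 v 0.25 | 0.27 v 0.23 | 0.21 v 0.19 |
| Boys, 54/64 | 0.43 v 0.35 | 0.37 v 0.32 | 0.28 v 0.26 |
| Girls, 45/57 | 0.47 v 0.38 | 0.40 v 0.34 | 0.31 v 0.28 |

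**Step 4: simulation check.** With gender, age and BMI in both models and no selective exclusion (2,000 runs per setting), the SE ratios were 1.238, 1.151, 1.083 and 1.024 for k = 1, matching the formula. Type I error was 4.2–5.7% for change and 4.3–5.8% for adjusted. In a separate 4,000-run check with a true effect of 0.30 SD, the mean estimates were 0.301 (change) and 0.300 (adjusted).

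**Step 5: dependence on baseline imbalance.** With the same covariates, adjusted minus change estimate = (1 − b) × covariate-adjusted baseline difference, where b is the fitted slope on the initial score. With equal SDs b is about r, so a 0.2 SD imbalance gives gaps of 0.14, 0.10, 0.06 and 0.02 SD at r = 0.3, 0.5, 0.7 and 0.9. The baseline t-test has little power to see such an imbalance: 0.2/0.1355 = 1.476, and Φ(1.476 − 1.96) is about 31%.

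**Step 6: BMI rule.** If no time-by-BMI term is fitted, dropping BMI leaves the time-by-group estimate unchanged. Otherwise (3,000 runs per setting) the SE cost was −0.2% to +2.3% for r of 0.3 to 0.7 when BMI acted alike at both times or on the final score only. It was 6.2–7.6% at r = 0.9 with BMI acting on the final score only. It was 2.8–19% across r of 0.3 to 0.9 when BMI effects of opposite sign were assumed at the two times. Type I error was 4.3–5.6% with the rule and 4.4–5.6% with BMI always included.

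**The case against.** The strongest reply is that nothing here is invalid. Time-by-group is a standard contrast, unbiased under randomisation, with type I error near 5%. That stands, and no bias is claimed.

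The size also rests on assumed r and k. The SE penalty runs from 1% to 41% over the ranges shown, is at most about 8% when r is 0.7 or more and the final SD is equal or larger, and vanishes when the true slope is 1. That stands too, so the claim is a usual gain of unknown size.

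The precision argument supposes a randomised comparison, whereas the analysed set lost 34.0% and 19.3% after allocation. This is a separate and larger problem that baseline adjustment does not cure. It is, however, also a reason to show both estimates.

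The identity in Step 5 is exact only when the two models share the same covariates and terms. Against the full gender-by-group model without BMI, under an assumed r of 0.6 and an effect differing by gender, it was off by about 0.014 SD on average and by up to 0.09 SD. The reconciliation must therefore be made between matched models.

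Finally, the Protocol reports the analysis in the past tense, so any new model is post hoc. This is accepted, and it is why the addition should be labelled as such and should not replace the stated result.

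**Conclusion.** The concern holds as a weakness of efficiency and transparency, not of validity. The stated analysis fixes the slope on the initial score at 1. With equal SDs and assumed r of 0.3 to 0.9, this forgoes precision worth 77 to 11 of the 220 children (220 − 143 to 220 − 209). The loss is smaller if the final SD exceeds the initial SD as in the k = 1.2 case, and larger if it is below it as in the k = 0.8 case. The actual loss cannot be fixed from the Protocol. A non-significant baseline t-test does not show that the change-score and adjusted results agree. The BMI rule is a minor point: usually a small cost, no measurable effect on type I error, but a covariate set that varies by outcome for no good reason. The addition is worth making because it is cheap, with medium confidence in how much it will gain.

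**What to change.** For every TGMD-2 outcome:

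1. Fit one fixed model of final score on group, initial score, gender, age and baseline BMI, with no selection on p-values. Report the adjusted between-group difference with its 95% CI.
2. Test group by gender in a separate second model and report boys and girls from it, so that the overall effect does not depend on how gender is coded.
3. Label this a post hoc baseline-adjusted analysis and show it beside the stated time-by-group result.
4. Report b and the covariate-adjusted baseline difference. Make the (1 − b) reconciliation against a change-score model with the same covariates and terms, and discuss any disagreement instead of choosing between the results.
5. State that neither model repairs the unequal exclusions.

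The cost is two further regressions per outcome, plus short matched fits for the reconciliation, all on data already collected. Step 1 uses at most two extra degrees of freedom (initial score, and BMI where it had been dropped) and step 2 uses one more. No new data are needed.
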